6.5.5 Clinical Laboratory Evaluation

Not applicable.

6.5.5.1 Liver Safety Assessment

Not applicable.

6.5.6 Vital Signs

For vital signs parameters: systolic blood pressure, diastolic blood pressure, pulse rate and body temperature, descriptive statistics will be used to summarize baseline value, post-baseline value and change from baseline at each specified post-baseline analysis visit by treatment group. Refer to Section [6.5.2](#) for the list of analysis visits excluding maximum.

6.5.7 Electrocardiograms

Not applicable.

6.6 Pharmacokinetic

Descriptive statistics (n, mean, SD, minimum, median, maximum, coefficient of variation (CV), geometric mean, and geometric CV) will be used to summarize baseline value, post-baseline value, and change from baseline at each post-baseline time point for serum concentrations of ASP0598 by treatment group including placebo using the SAF.

Analysis time points:

SAD: Baseline, Day 1 0.5 hour post dose, Day 1 1 hour post dose and Day 3 (Cohorts 1, 2, and 3.) or Day 2 (Cohorts 4, 5, and 6).

MAD: Baseline, Day 1 0.5 hour post dose, Day 1 1 hour post dose, Week 4 predose, Week 4 0.5 hour post dose, Week 4 1 hour post dose.

Dose expansion: Not Applicable.

6.7 Other Analyses

No other analyses are planned.

6.8 Interim Analysis (and Early Discontinuation of the Clinical Study)

Two interim analyses are planned and will be conducted after completion of the last cohort of the SAD and MAD, respectively. The decision to open the single dose expansion and multiple dose expansion will be made based on the safety and efficacy results of the above interim analyses. During each interim analysis, the Data Monitoring Committee (DMC) team will review the data and make the final decision to open the dose expansion. Three different treatment groups including placebo or two different treatment groups including placebo will be selected to open the expansion phase. Additional details and analyses will be described in a DMC charter/an IAP.

6.9 Additional Conventions

6.9.1 Analysis Windows for Safety Variables

For the assessments where the summaries and/or analyses are presented by analysis visit during study period, post baseline values will not contribute to the safety analyses:

- SAD: if the study day of the value is > minimum(study day of end of study visit, 57) + 7 days.
- Single dose expansion and MAD: if the study day of the value is > minimum(study day of end of study visit, 85) + 7 days.
- Multiple dose expansion: if the study day of the value is > minimum (study day of end of study visit, 113) + 7 days.

For the assessments where the summaries and/or analyses are not presented by analysis visit during study period (AEs, previous and concomitant medications and modified brighton grading scheme), end day of end of study visit is defined as follows:

- SAD: minimum(study day of end of study visit, 57) + 7 days.
- Single dose expansion and MAD: minimum(study day of end of study visit, 85) + 7 days.
- Multiple dose expansion: minimum (study day of end of study visit, 113) + 7 days.

6.9.1.1 Duplicate Values on the Same Day

If more than one value is reported on the same day, then the value based on the following convention will be used for analysis visit window programming. This needs to be done before creating the analysis visits or time points.

Variable Type	Assessment	Convention
Continuous variable	Bone Conduction by PTA	Last value on that day based on non-missing time. If time is missing for all values on the same day, then the value corresponding to the scheduled visit will be used.
	TVAS	
	Vital Signs	
Categorical variable	Microscopic ear examination	Last value on that day based on non-missing time. If time is missing for all values on the same day, then the value corresponding to the scheduled visit will be used.

6.9.1.2 Analysis Visit Windows

Table 4 Analysis Visit Windows: Bone Conduction by PTA, TVAS, Microscopic Ear Examination and Vital Signs

Analysis Visit	Target Study Day	Analysis Visit Window (Study Day)			
		SAD	Single dose expansion	MAD	Multiple dose expansion
Baseline ^a	1	≤ 1	≤ 1	≤ 1	≤ 1
Day 2 ^b	2	2	NA	NA	NA
Day 2 ^c	2	2 to 3	NA	NA	NA
Day 3 ^d	3	3 to 4	NA	NA	NA
Week 1	8	5 to 11	NA	2 to 11	NA
Week 2	15	12 to 18	2 to 18	12 to 18	2 to 22
Week 3	22	NA	NA	19 to 25	NA
Week 4	29	19 to 39	19 to 39	26 to 32	23 to 36
Week 5	36	NA	NA	33 to 39	NA
Week 6	43	NA	NA	NA	37 to 50
Week 8	57	≥ 40	40 to 74	40 to 74	51 to 71
Week 12	85	NA	≥ 75	≥ 75	72 to 99
Week 16	113	NA	NA	NA	≥ 100
Minimum ^e		≥ 2	≥ 2	≥ 2	≥ 2
Maximum ^f		≥ 2	≥ 2	≥ 2	≥ 2
EOS ^g		≥ 2	≥ 2	≥ 2	≥ 2

^a Baseline value for the above data is based on the last available non-missing value on or prior to the first dose day (Day 1) of study drug within the visit window.

^b For cohorts 1, 2 and 3.

^c For cohorts 4, 5 and 6.

^d Day 3 evaluations will only be performed for cohorts 1, 2 and 3.

^e Minimum value for the above data is based on the minimum of non-missing post-baseline value within the visit window.

^f Maximum value for the above data is based on the maximum of non-missing post-baseline value within the visit window.

^g EOS value for the above data is based on the last available non-missing post-baseline value within the visit window.

For microscopic ear examination, 1 hour post dose analysis timepoint on dosing days will be assigned same as the nominal timepoint.

To identify the value for the analysis, the following rules will apply excluding baseline, minimum, maximum and EOS:

1. For an analysis visit, if a subject has more than one result with a value included within a window, the value closest to the target study day will be used. In case of ties between values located on different sides of the target study day, the later assessment will be used.

2. For the categorical parameter, if a subject has more than one result included within a window, the assessment closest to the target study day will be used. In case of ties between results located on different sides of the target study day, the later assessment will be used.

Planned time points will be used as analysis time points. Concentrations will be excluded from analysis if the actual time from dosing (actual sample date/time – dose date/time) is outside the time window as specified below.

Table 5 Analysis Visit Windows: Serum ASP0598 or Placebo Concentrations

Analysis Time Point	Analysis Time Window
Baseline (Pre-dose)	Actual time from dosing ≤ 0
0.5 hour post dose	Actual time from dosing = 30 ± 5 minutes
1 hour post dose	Actual time from dosing = 60 ± 5 minutes

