7.2.3 Vital Signs

Vital signs will include systolic and diastolic blood pressure (mmHg), heart rate (bpm), and body temperature (°F / °C). Vital signs will be performed according to the Schedule of Assessments ([Table 2](#), [Table 3](#), [Table 4](#), [Table 5](#)). Additional vital sign assessments may be taken as indicated or according to institutional standard procedure.

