9 STATISTICAL METHODOLOGY

A statistical analysis plan (SAP) will be written to provide details of the analysis, along with specifications for tables, listings and figures to be produced. The SAP will be finalized before the database lock. Any changes to the dose escalation of the SAP will be approved prior to

unblinding the dose escalation data for the prescribed interim analysis. Changes from the planned analyses in the final SAP that impact the statistical analyses will be justified in the clinical study report (CSR).

In general, continuous data will be summarized using descriptive statistics (number of subjects, mean, standard deviation and/or standard error, minimum, median and maximum), and categorical data will be summarized using number and percentage of subjects. Baseline will be defined as the last non-missing observation on or prior to the administration of study drug, unless otherwise specified.

For SAD and MAD, results will be presented by ASP0598 treatment group in each cohort and placebo group where placebo subjects will be pooled across cohorts.

For single dose expansion and multiple dose expansion, results will be presented by ASP0598 treatment group and placebo group.

All statistical comparisons between ASP0598 and placebo will be made using a 2-sided test at $\alpha = 0.05$ significance level and 2-sided 95% confidence intervals (CIs) will be reported for each treatment group and difference from placebo.

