| PET | Positron emission tomography |
| PK | Pharmacokinetic |
| PTA | Pure Tone Audiometry |
| PT | Preferred Term |
| QA | quality assurance |
| QC | quality control |
| RBC | red blood cell |

| Abbreviations | Description of abbreviations |
|----------------------|--|
| RNA | Ribonucleic acid |
| RSI | reference safety information |
| (S)AE | serious adverse event or adverse event |
| SAD | Single Ascending Dose |
| SAE | serious adverse event |
| SAF | Safety analysis set |
| SAP | Statistical analysis plan |
| SDV | source document verification |
| SE | Standard error |
| SFL | screen failure log |
| SOC | System organ class |
| SOP | standard operating procedure |
| SPC | summary of product characteristics |
| SUSAR | suspected unexpected serious adverse reactions |
| TEAE | treatment-emergent adverse event |
| TBL | total bilirubin |
| TM | Tympanic membrane |
| TMF | Trial Master File |
| TMP | Tympanic membrane perforation |
| TVAS | Tinnitus visual analog scale |
| ULN | upper limit of normal |
| USM | Urgent safety matter |
| WBC | white blood cell |
| WOCBP | Women of child bearing potential |
| µg | microgram |

Definition of Key Study Terms

| Terms | Definition of Terms |
|------------------------|---|
| Baseline | Assessments of subjects as they enter a study before they receive any treatment. |
| Endpoint | Variable that pertains to the efficacy or safety evaluations of a study. Note: Not all endpoints are themselves assessments since certain endpoints might apply to populations or emerge from analysis of results. That is, endpoints might be facts about assessments (e.g., prolongation of survival). |
| Enroll | To register or enter a subject into a study. Note: Once a subject has received the IP or placebo, the protocol applies to the subject. |
| Intervention | The drug, device, therapy or process under investigation in a study that is believed to have an effect on outcomes of interest in a study (e.g., health-related quality of life, efficacy, safety and pharmacoeconomics). |
| Investigational period | Period of time where major interests of protocol objectives are observed, and where the test product or comparative drug (sometimes without randomization) is given to a subject and continues until the last assessment after completing administration of the test product or comparative drug. |

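### The SAP sets baseline by dosing day, not dosing time, so a bone conduction, TVAS or vital-sign value recorded after dosing on Day 1 would become that subject's baseline

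*SAP*

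**What the plan says.** Protocol section 9 gives the general rule: "Baseline will be defined as the last non-missing observation on or prior to the administration of study drug, unless otherwise specified". The protocol's list of key terms (12.12) describes baseline as "Assessments of subjects as they enter a study before they receive any treatment". Both refer to treatment, not to a calendar day.

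SAP 6.9.1.2, Table 4, covers bone conduction, TVAS, the microscopic ear examination and vital signs. Its baseline window is study day 1 or earlier, and footnote a takes the "last available non-missing value on or prior to the first dose day (Day 1) of study drug within the visit window". Table 7 repeats this footnote for the efficacy PTA assessments and tympanometry.

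Where several values fall on one day, SAP 6.9.1.1 keeps the "Last value on that day based on non-missing time". If none of that day's values has a time, it keeps the one from the scheduled visit. This step comes before analysis visits are assigned, and it names PTA, TVAS and vital signs.

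Every post-baseline window in Table 4 starts on Day 2 or later. That includes Maximum, for which the footnote says: "Maximum value for the above data is based on the maximum of non-missing post-baseline value within the visit window".

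The SAP handles post-dose data explicitly in three other places:
- Microscopy, in 6.9.1.2: "For microscopic ear examination, 1 hour post dose analysis timepoint on dosing days will be assigned same as the nominal timepoint".
- Imaging: Table 6 excludes the scheduled post-dose images on dosing days.
- Pharmacokinetics: Table 5 defines baseline by actual time from dosing.

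**The concern.** A day-based baseline is harmless only if nothing is measured between dosing and the end of Day 1. For PTA, TVAS and vital signs the SAP has no rule for that interval. A timed post-dose value displaces the pre-dose one under the same-day rule, enters the baseline window, and can enter no post-baseline window.

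Change from baseline in bone conduction and in TVAS are primary safety endpoints (Protocol 3.1). The same baseline feeds three counts: increases of at least 20 dB, increases of at least 10 dB at two consecutive frequencies (both SAP 6.5.2), and TVAS increases (SAP 6.5.3). An acute effect absorbed into baseline shows as no change, and recovery from it shows as improvement. In SAD, with four active subjects per cohort, one such subject is visible in the table.

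**Working it through.** The documents state no figure to reproduce. The check applies both rules to the same records.

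**Rules**
- SAP: B = last value with study day ≤ 1, keeping the latest timed value within Day 1 (Table 4 footnote a with 6.9.1.1).
- Protocol: B = last value at or before the time of administration (section 9).
- Change at a visit = value at that visit − B.

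**Bone conduction.** The values are assumed for illustration: mean 20 dB at screening and before dosing, 40 dB after dosing. The threshold is the 20 dB increase in SAP 6.5.2.

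| Case | Day 1 values (dB) | Day 2 value | SAP: B and change | Protocol: B and change |
|---|---|---|---|---|
| A | 20 pre-dose only | 40 | 20; 40 − 20 = +20 | 20; 40 − 20 = +20 |
| B | 20 pre-dose, 40 post-dose | 40 | 40; 40 − 40 = 0 | 20; 40 − 20 = +20 |
| C | 40 post-dose only | 40 | 40; 40 − 40 = 0 | 20 (screening); 40 − 20 = +20 |
| D | 20 pre-dose, 40 post-dose | 20 | 40; 20 − 40 = −20 | 20; 20 − 20 = 0 |

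In A the rules agree. In B and C the 20 dB flag is raised under the protocol rule and lost under the SAP rule. In D the SAP rule reports an improvement that did not happen. Correcting baseline removes that false improvement, but the 40 dB reading on Day 1 still counts nowhere, because Maximum starts at Day 2.

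**TVAS, also assumed.** Treated ear in SAD: 0 before dosing, 5 on a timed post-dose Day 1 repeat, 5 on Day 2, 0 at Week 2.
- Protocol rule: B = 0; changes 5 − 0 = +5 and 0 − 0 = 0. One increase is counted.
- SAP rule: B = 5; changes 5 − 5 = 0 and 0 − 5 = −5. No increase is counted.

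**Weight of one subject.** In a SAD active cohort, 1/4 = 25%. In a MAD active cohort, 1/6 = 17%, and in an expansion arm, 1/13 = 8%. The Day 2 examples apply only to SAD. The first visit after Day 1 is Day 8 in MAD and Day 15 in the expansion parts, so a shift would have to last until then for a flag to be lost.

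**Can a post-dose Day 1 value arise?**
- Each schedule (Protocol Tables 2 to 5) has one Day 1 entry for PTA, TVAS and vital signs, with no post-dose repeat.
- Those entries carry no pre-dose footnote, unlike imaging, microscopy and the PK sample.
- Protocol 7.2.8 leaves the order of assessments to flow-chart figures, which were not readable in the text used here. In the Figure 7 footnotes, PTA is lettered a and administration b, which suggests that PTA comes first. That is only an inference.
- Extra vital signs are expressly permitted: "Additional vital sign assessments may be taken as indicated or according to institutional standard procedure". No equivalent provision for a repeat audiogram or TVAS was found.
- The imaging and microscopy schedule keeps subjects under assessment until about 60 minutes after dosing.

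**The case against.** The strongest reply is that the SAP's post-dose rules match the planned data. Images, the one-hour microscopy and PK are the measurements scheduled after dosing on Day 1, and each has a timepoint rule. PTA, TVAS and vital signs are scheduled once, probably before dosing, so both definitions give the same baseline. This stands, and it limits the point to unscheduled repeats and late Day 1 assessments.

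Four further replies have weight:
- The protocol's rule allows for other specification, so a SAP-specific baseline is not in itself a breach. Even so, the SAP gives no reason for a looser rule, and its lists of changes mention none.
- If no Day 1 value has a time, the scheduled value is kept and an untimed repeat does no harm. This does not help when only the repeat is timed, or when the scheduled assessment was itself late.
- Under SAP 5.1, a Day 1 adverse event counts as treatment-emergent if its onset is marked as after the dose or the box is left blank. Tinnitus, vertigo, dizziness and sudden hearing loss are terms of special interest in SAP Appendix 2. A symptom reported as an adverse event is therefore still counted. That does not correct the change-from-baseline tables, and it does not capture an audiometric shift that nobody reported as an event.
- The explicit permission for repeats covers only vital signs, which are exploratory. The same-day rule does, however, foresee duplicate PTA and TVAS values.

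A reader might infer that the plan as scheduled hides acute ototoxicity. The documents do not support that: no post-dose Day 1 audiogram or TVAS is planned, and the adverse-event route remains open. Nor do they support extending the point to the scheduled post-dose images, which Table 6 already excludes.

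**Conclusion.** The point holds as a conditional gap in a derivation rule. If a PTA, TVAS or vital-sign value is recorded after dosing on Day 1 and selected by the same-day rule, the SAP makes it the baseline. That departs from protocol section 9, and the subject's change from baseline is wrong by the difference between the post-dose and pre-dose values. Under the assumed figures, that is 20 dB or 5 TVAS points, with loss of a threshold count in cases B and C.

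Without such a value there is no effect. The documents give no frequency for such values, so no expected number of affected subjects can be stated. Sample size, power and alpha are untouched. Priority is low to moderate: the affected endpoints include two primary ones and the cohorts are small, but the trigger is not a planned event.

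**What to change.** 1. In footnote a of SAP Tables 4 and 7, define baseline as the last non-missing value on or before the date and time of first administration.
2. In SAP 6.9.1.1 and the matching rule in 6.9.2.1, apply the same-day rule on Day 1 to pre-dose values only.
3. Use a Day 1 value without a time only if it is the scheduled assessment.
4. List post-dose Day 1 values separately, or extend the Maximum window explicitly to include them. The second option changes the Table 4 windows as well as the footnote.

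Table 6 needs no change for the scheduled post-dose images.

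The cost is minor wording and programming. Dose time must be available in the data. Dose escalation already needs it for the PK windows, but the expansion parts have no PK sampling, so its collection there should be confirmed. Clock times for PTA, TVAS and vital signs on Day 1 are also needed for the rule to work beyond the untimed default.

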6.9.1.3 Value Below Limit of Quantification

1) Serum concentration values (ASP0598 or Placebo) below limit of quantification (BLQ) will be set to 0 for the calculation of summary statistics. Geometric mean and Geometric CV will not be calculated if at least 1 concentration value is equal to 0.

2) If more than 50% of the concentrations are BLQ at a given time point, SD and CV will not be calculated in the summary statistics.

6.9.2 Analysis Windows for Efficacy Variables

For the assessments where the summaries and/or analyses are presented by analysis visit during study period, post baseline values will not contribute to the efficacy analyses:

- SAD: if the study day of the value is $> \text{minimum(study day of end of study visit, 57)} + 7$ days.
- Single dose expansion and MAD: if the study day of the value is $> \text{minimum(study day of end of study visit, 85)} + 7$ days.
- Multiple dose expansion: if the study day of the value is $> \text{minimum(study day of end of study visit, 113)} + 7$ days.

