| Medical History/Disease History/Demographics | | X | X | | | | | |
| Physical Exam including Height and Weight | | X | | | | | | |
| Vital Signs ^a | Remote/Virtual/Telemedicine Visits allowed. | X | X | X | X | X | X | X |
| Prior/Concomitant Medications ^b | | X | X | X | X | X | X | X |
| Adverse Events Assessment ^c | | X | X | X | X | X | X | X |
| ASP0598 or placebo | | | X ^d | | | | | |
| Microscopic Ear Examination | If delayed, should be completed as soon as possible | X ^e | X ^f | X ^g | X ^g | X ^g | X ^g | X ⁱ |
| Modified Brighton Grading Scheme Evaluation | | | X ^f | X | X | X | X | X |
| Imaging picture of tympanic membrane by endoscope | | X ^e | X ^h | X | X | X | X | X |
| Bone conduction by Pure Tone Audiometry (PTA) | | X ^e | X | X ^j | X ^j | X ^j | X ^j | X |
| Air conduction by PTA | | X ^e | X | | | | | X |
| Tympanometry | | X ^e | X | | | | | X |
| Tinnitus Visual Analog Scale (TVAS) | Remote/Virtual/Telemedicine Visits allowed for non-dosing visits. | X | X | X | X | X | X | X |

Table continued on next page

| Day | Alternative Approach | Screening | Randomization | Observation | | | | |
|----------------------------------|--|-----------|----------------|-------------------|--------|------------|------------|------------|
| | | | | Day -28 to Day -1 | Day 1 | Day 2 | Day 8 | Day 15 |
| Week | | | | | | Week 1 | Week 2 | Week 4 |
| Visit Windows | | | | | +1 day | +/- 3 days | +/- 3 days | +/- 3 days |
| Visit number | | 1 | 2 | 3 | 4 | 5 | 6 | 7 |
| Serum Chemistries | Visit collection of samples at local facility is acceptable if results can be made available to investigative site | X | | | | | | |
| CBC with Differential | | X | | | | | | |
| Pregnancy Test ^k | | X | X | | | | | X |
| Pharmacokinetic Sample | | | X ¹ | X | | | | |
| Blood Sample for Future Analysis | | | X | | | | | X |
| Urinalysis | Visit collection of samples at local facility is acceptable if results can be made available to investigative site | X | | | | | | |

AE: adverse event; CBC: complete blood count; EOS: end of study; PK: pharmacokinetic; SAD: Single Ascending Dose; TM: tympanic membrane

- a. Vital Signs include blood pressure, body temperature, and heart rate.
- b. Includes all medications taken within 28 days prior to ASP0598 Otic Solution or placebo administration at Day 1.

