4.1 Full Analysis Set

The full analysis set (FAS) will consist of all randomized subjects who receive a dose of

study drug and have baseline value and at least 1 post baseline complete closure assessment during study period. This will be the primary analysis set for efficacy analyses.

In the analyses of FAS, subjects will be presented by randomized (planned) treatment group even if the treatment they received was different.

For study period, post baseline values will not contribute to the FAS as shown below:

- SAD: if the study day of the value is > minimum(study day of end of study visit, 57) + 7 days.
- Single dose expansion and MAD: if the study day of the value is > minimum(study day of end of study visit, 85) + 7 days.
- Multiple dose expansion: if the study day of the value is > minimum(study day of end of study visit, 113) + 7 days.

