5.3 Secondary Efficacy Endpoints

SAD and Single dose expansion

Categorical endpoint:

- Complete closure of Tympanic Membrane Perforation (TMP) at Week 8 for SAD and at Week 12 for single dose expansion

TMP complete closure observed response:

Using the non-missing result of complete closure of TMP, an observed response is

Yes: if a subject with complete closure of TMP,

No: if the above condition is false.

TMP complete closure imputed response at Week 8 for SAD:

Using the non-missing result at Week 8, an imputed response is same as observed response at Week 8.

If a response is missing at Week 8, assign the latest post baseline observed response available prior to Week 8.

TMP complete closure imputed response at Week 12 for single dose expansion (Primary analysis imputation):

For endpoint #1 defined in Section [5.3.2](#), using the non-missing result at Week 12, an imputed response is

No intercurrent events (ICE) occurs: same as observed response at Week 12,

ICE occurs: assign the latest post baseline observed response available just before the ICE.

TMP complete closure imputed response at Week 12 for single dose expansion (Sensitivity analysis imputation):

For endpoint #1 defined in Section [5.3.2](#), using the non-missing result at Week 12, an imputed response is

No ICE occurs: same as observed response at Week 12,

ICE occurs: No.

Continuous endpoints:

- Change from baseline in the ratio of TMP size per total area of tympanic membrane at Week 8 for SAD and at Week 12 for single dose expansion

Ratio of TMP size per total area of tympanic membrane (%):

$$[\text{TMP Size} \div \text{Periphery of the Tympanic Membrane Region of Interest (ROI)}] \times 100$$

- Change from baseline in TMP size at Week 8 for SAD and at Week 12 for single dose expansion

Here TMP size = TMP ROI from imaging data.

MAD and Multiple dose expansion

Categorical endpoint:

- Complete closure of TMP at Week 12 for MAD and at Week 16 for multiple dose

expansion

TMP complete closure observed response:

Using the non-missing result of complete closure of TMP, an observed response is

Yes: if a subject with complete closure of TMP,

No: if the above condition is false.

TMP complete closure imputed response at Week 12 for MAD:

Using the non-missing result at Week 12, an imputed response is same as observed response at Week 12.

If a response is missing at Week 12, assign the latest post baseline observed response available prior to Week 12.

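### The SAP's data cut-off, the smaller of the end-of-study day and the target day plus 7, drops a final visit 8 or more days late and ends that subject's TEAE period before the visit takes place

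*SAP*

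**What the plan says.** **The cut-off.** SAP 6.9.2 states that "post baseline values will not contribute to the efficacy analyses" if their study day is later than the smaller of the EOS visit day and the target day, plus 7. The target is Day 57 for SAD, Day 85 for single dose expansion and MAD, and Day 113 for multiple dose expansion. SAP 4.1 repeats the limit: "For study period, post baseline values will not contribute to the FAS as shown below". SAP 6.9.1 applies it to safety data shown by visit.

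**Adverse events.** SAP 5.1 counts a TEAE up to the EOS visit and refers to 6.9.1 for the end day of that visit. There the end day is, for example, "Single dose expansion and MAD: minimum(study day of end of study visit, 85) + 7 days". Protocol 9.5.1 ends the TEAE period at the EOS visit. Protocol 7.3.1 collects AEs for 14 days after the last visit.

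**Visit windows.** SAP Table 6 (imaging) prints the last window as Day 40 or later (SAD), 75 or later (single dose expansion, MAD) and 100 or later (multiple dose expansion), with no upper bound. Tables 4 and 7 do the same for safety measures, audiometry and tympanometry. The protocol schedules allow 3 days either side of target.

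**Closure status.** For single dose expansion SAP 5.3 says "No ICE occurs: same as observed response at Week 12", with the matching rule at Week 16 for multiple dose expansion. For SAD and MAD it carries the latest earlier response forward.

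**The concern.** A cut-off normally keeps stray data from well after a subject has finished out of the analysis. Because this one takes the smaller of two days, it can fall before the subject's own last visit. Data from a planned assessment, collected and in the database, then do not count.

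Two things are at stake.

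- **Primary safety endpoints.** TEAEs, bone conduction and tinnitus are all affected. An event that starts after the cap but before the EOS visit leaves the TEAE tables. The last hearing and tinnitus values leave the by-visit summaries and the maximum during the study.
- **Closure in the expansion parts.** This is the efficacy endpoint with the hierarchical test. A subject who drops out keeps the last status before the intercurrent event. A subject who completes, but late, has no status at all.

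**Working it through.** **1. The plan's own sample size.** Inputs from SAP 3: closure 10% against 80%, two-sided 0.05, 11 per group for more than 90% power, 13 enrolled per group after 10% drop-out. The plan does not name the test. Enumerating the two-sided Fisher exact test gives 90.5% at 11 per group and 84.1% at 10. Drop-out: 11 / 0.9 = 12.2, rounded up to 13. The stated figures reproduce.

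**2. The cap.** Cut-off = min(EOS day, target) + 7. The protocol window ends at target + 3.

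| Part | Target | Protocol window ends | Latest usable day | First final-visit day lost | Days past protocol window |
|---|---|---|---|---|---|
| SAD | 57 | 60 | 57 + 7 = 64 | 65 | 65 - 60 = 5 |
| Single dose expansion, MAD | 85 | 88 | 85 + 7 = 92 | 93 | 93 - 88 = 5 |
| Multiple dose expansion | 113 | 116 | 113 + 7 = 120 | 121 | 121 - 116 = 5 |

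**3. Single dose expansion, by EOS day.**

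| EOS day | Cut-off | EOS values | TEAE period relative to EOS |
|---|---|---|---|
| 55 (early termination) | 55 + 7 = 62 | kept | ends 7 days after |
| 85 | 92 | kept | ends 7 days after |
| 88 | 92 | kept | ends 4 days after |
| 92 | 92 | kept | ends on the day |
| 95 | 92 | dropped | ends 3 days before; onsets on Days 93 to 95 not counted |

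**4. What replaces a lost final value.**

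- *Closure, SAD and MAD:* the latest earlier response (SAP 5.3).
- *Closure, expansion:* nothing. A late completer has no intercurrent event under SAP 5.3.1. The primary and sensitivity rules then both use the observed Week 12 or 16 result. No other scheduled visit can fill the window: the preceding ones end at Day 57 + 3 = 60 (window opens at 75) and Day 85 + 3 = 88 (window opens at 100).
- *TMP size and ratio, expansion:* the MMRM uses earlier visits under missing at random, and the imputation in SAP 6.9.3.5 covers data missing for other reasons.
- *Air conduction and tympanometry:* in SAD, single dose expansion and MAD the final visit is the only scheduled post-baseline assessment (Protocol Tables 2 to 4), so no post-baseline result remains.
- *Bone conduction and tinnitus:* the EOS row falls back to an earlier visit.

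**5. Windows with the cap applied.** They become 40 to 64, 75 to 92 and 100 to 120. Days allowed early and late around target: SAD 57 - 40 = 17 and 7; single dose expansion and MAD 85 - 75 = 10 and 7; multiple dose expansion 113 - 100 = 13 and 7. The single dose expansion Week 8 window runs to Day 74, which is 74 - 57 = 17 days late. The SAP gives no reason for the tighter late side at the final visit.

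**6. Size.** One subject is 1/13 = 7.7% of an expansion arm. Fisher exact power by evaluable subjects in each group: 13, 97.0%; 12, 94.6%; 11, 90.5%; 10, 84.1%. Power falls below 90% once three per group are lost.

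**The case against.** The strongest defence is that 6.9.2 is a general filter, used consistently in 4.1 and 6.9.1, and that Table 6 only assigns what passes it. The late limit is already more than twice the protocol's 3 days, and an upper bound keeps a Week 12 result close to Week 12. This stands in part. A reader might infer that the cut-off contradicts Table 6. It does not: the two can be applied in sequence. The defect there is a bound that the tables do not show and the SAP does not justify.

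Other stronger readings also fail.

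- **Escalation cohorts lose closure results.** They do not; SAD and MAD closure is carried forward and is not tested.
- **Late AEs are deleted.** Only onsets after the cap leave the TEAE tables; nothing says that they leave the data. For subjects seen on time, the SAP period runs past the EOS visit.
- **The protocol routinely invites late examinations.** The instruction "If delayed, should be completed as soon as possible" stands in Protocol 12.11, which applies only in a crisis and after discussion with the medical monitor. It shows that late visits can occur, not that they will be common. The same appendix asks for critical out-of-window assessments to be identified.
- **The EOS visit is the only one at which the ear may be cleaned.** Earlier cleaning is permitted when necessary.

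It is also fair that the closure gap comes from SAP 5.3 having no rule for a missing result without an intercurrent event. That gap exists for any missed final image, and moving the cut-off does not close it.

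The defence does not answer the TEAE point. An end day of the EOS visit that falls before the EOS visit does not fit Protocol 9.5.1.

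**Conclusion.** The point holds in a limited form. A final visit 8 or more days after target is discarded by the SAP's own rule. For that subject the TEAE period ends before the EOS visit, contrary to the protocol definition, and the final safety and hearing values are lost. In the expansion parts there is also no closure status at the tested time point.

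Subjects seen within 7 days after target, and early terminators, lose nothing from the EOS visit. FAS membership is unaffected where an earlier closure assessment exists.

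The documents do not say how often a final visit will be that late; the number is probably small. The sample size calculation is unaffected. The power figures assume the planned closure rates, an unstratified Fisher test and equal losses in both groups. The change is worth making because the rule removes primary safety data and is cheap to correct, not because a large loss is expected.

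**What to change.** - **SAP 6.9.1:** define the end day so that it is never earlier than the actual EOS visit, for example EOS day + 7. AEs with onset up to the EOS visit then count as TEAEs, and the EOS safety values stay in. Do not extend TEAEs to the end of AE collection: that runs 14 days past the last visit and would itself depart from Protocol 9.5.1.
- **SAP 4.1 and 6.9.2:** base the cut-off on the actual EOS day, so that the final image, audiometry and tympanometry are kept. Cross-reference the cut-off from Tables 4, 6 and 7.
- **Sensitivity:** flag final visits outside the protocol's 3-day window and repeat the closure analysis without them.

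The cost is SAP wording and one extra closure table. The drawback is that a few late values enter the Week 8, 12 or 16 analysis; the sensitivity analysis shows whether they matter.
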